## 1. Study Synopsis

Title of clinical trial	Omega 3 and Vitamin D dosage in a population with moderate to high risk of AMD
Protocol Short Title/Acronym	OVID-AMD
Sponsor name	UZ Leuven
Principal Investigator	[name]
Medical condition or disease under investigation	AMD
Purpose of clinical trial	Blood serum dosage of omega 3 and vitamin D in individuals with moderate and high risk of AMD as determined by STARS scores of $\geq 10$
Primary objective	To detect individuals at high and moderate risk of AMD in the Belgium population and to perform a blood serum dosage of omega 3 and Vitamin D
Secondary objective (s)	Dosage of zinc oxide and cupric oxide
Trial Design	Multi-centric, epidemiological and interventional survey

Endpoints	Blood dosage of omega 3 and Vitamin D, zinc oxide and cupric oxide
Sample Size	Not applicable
Summary of eligibility criteria	
 
- subjects <math>\geq</math> 55 years
 
- subjects with family history of AMD
 
- age-related maculopathy present
 
- no previous intake of eye nutritional supplements < 4 months prior to enrollment
 
- no current intake of multivitamins especially when containing Vit D
 

Maximum duration of treatment of a Subject	1 visit
Version and date of final protocol	
Version and date of protocol amendments	

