### 4. Selection and withdrawal of subjects

#### 4.1 Inclusion criteria

\* Subjects > 55 years

\* STARS questionnaire score  $\geq 10$  (moderate to high risk for AMD)

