#### 4.2 Exclusion criteria

- Previous intake of eye nutritional supplements < 4 months prior to enrollment (half-life 25-OH D = 3-4 weeks, half-life of red blood cells: 100-120 days)
- STARS questionnaire score < 10 (low risk for AMD)
- Patient with AMD (stage 3 and 4)

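### The synopsis and Section 4 give different eligibility lists, and the bar on current multivitamins, which bears on serum vitamin D, is missing from Section 4

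*Combined protocol and SAP*

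**What the plan says.** The eligibility row of the Study Synopsis has five items:

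- age 55 or over
- "subjects with family history of AMD"
- "age-related maculopathy present"
- no eye supplements in the 4 months before enrolment
- "no current intake of multivitamins especially when containing Vit D"

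The STARS threshold of 10 is not among them. It is in the synopsis row on the purpose of the trial, where risk is "as determined by STARS scores of" 10 or more.

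Section 4.1 has two inclusion criteria: "Subjects > 55 years" and a "STARS questionnaire score" of at least 10. Section 4.2 has three exclusions: "Previous intake of eye nutritional supplements < 4 months prior to enrollment", a STARS score below 10, and AMD of stage 3 or 4. It supports the supplement window with two figures: "half-life 25-OH D = 3-4 weeks" and a red blood cell half-life of 100-120 days. Neither 4.1 nor 4.2 mentions multivitamins or any vitamin D intake other than through eye supplements.

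The trial is multi-centric (Section 3.2), has one visit (Section 5.1) and expects 50 subjects (Section 8.1).

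**The concern.** A summary may leave out detail from the full list. It should not contain a criterion that the full list lacks, because a centre working from the full list will then not apply it. That is the position of the multivitamin restriction.

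Vitamin D intake bears directly on what is measured. Serum vitamin D is in the title, the primary objective and the endpoints, and Section 8.2 defines categories for it alone (cut-offs at 30, 50 and 125 nmol/L). If centres screen from different lists, the reported vitamin D distribution describes a mixture of populations. The study has no control group that might offset this, and its results are meant to inform a larger study.

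The users might also not be identifiable afterwards. The flowchart (Section 3.3) and Sections 5.1 to 5.3 have no item for multivitamin or vitamin D intake. The electronic patient file may hold the information, but Sections 12 and 13 do not say so, and the paper CRF is described only as collecting questionnaires.

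**Working it through.** **1. The two lists side by side**

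| Item | Synopsis | Sections 4.1 and 4.2 | Result |
|---|---|---|---|
| Age | 55 or over | over 55 | direct conflict |
| Family history of AMD | listed | absent | synopsis only |
| Age-related maculopathy | listed | absent | synopsis only |
| Current multivitamins | not allowed | absent | synopsis only |
| Eye supplements, 4 months | not allowed | not allowed | agree |
| STARS 10 or more | purpose row only | required | different row, no conflict |
| AMD stage 3 and 4 | absent | excluded | Section 4.2 only |

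The age conflict affects only people aged exactly 55. For family history and maculopathy, the synopsis does not say whether both are required, either is enough, or they are examples, so their effect on entry cannot be determined. The stage 3 and 4 exclusion may simply have been left out of a summary.

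**2. What the 4-month window achieves on the protocol's own half-life**

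The inputs are the 25-OH D half-life of 3-4 weeks and the 4-month window, both from Section 4.2. I assume first-order elimination. The fraction remaining is 2^(−t/half-life).

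- 4 months = 121.75 days = 17.4 weeks.
- Half-life 4 weeks: 17.4/4 = 4.35 half-lives; 2^(−4.35) = 4.9%.
- Half-life 3 weeks: 17.4/3 = 5.80 half-lives; 2^(−5.80) = 1.8%.
- If 4 months is read as 16 weeks: 16/4 = 4.0 half-lives, 6.25%; 16/3 = 5.33 half-lives, 2.5%.

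These are upper limits, reached by someone who stopped exactly 4 months before enrolment. For a current multivitamin user admitted under Section 4 the elapsed washout is zero.

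**3. Weight of one subject**

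1/50 = 2 percentage points of any reported share. The documents do not give the proportion of multivitamin users or their vitamin D intake, so the shift in the results cannot be calculated.

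**4. Precision lost if users are left out of a supplementary table**

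At a share of 50% the 95% Wilson half-width is z/(2√(n + z²)), with z = 1.96 and z² = 3.84.

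- n = 50: 0.98/√53.84 = 13.4 points
- n = 45: 0.98/√48.84 = 14.0 points
- n = 40: 0.98/√43.84 = 14.8 points

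The 5 and 10 users implied by n = 45 and n = 40 are illustrative assumptions. The plan itself specifies no interval.

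**The case against.** The synopsis is Section 1 of the same protocol, and nothing in Section 4 permits multivitamins. Read cumulatively, the criteria exclude current users, so the harm depends on a centre screening from Section 4 alone. It is fair that the multivitamin item is an omission and that age is the only literal contradiction. The risk remains, because Section 4 presents itself as the full set of inclusion and exclusion criteria and no order of precedence is given.

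The 4-month window also rests on the red-cell figure. About 122 days is close to 100-120 days, so that figure may be what set its length. This stands. The half-life calculation shows what the window achieves for vitamin D, and does not show that vitamin D alone determined it. It is still true that Section 4.2 cites 25-OH D elimination as a reason for a washout and leaves current multivitamin use unaddressed.

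The half-life and Wilson figures do not measure the effect of the gap, which is correct. Without the number of users, one can say only that the vitamin D results could be affected.

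Applying the eye-supplement exclusion already requires some intake history at screening, and the content of the CRF is not shown. That makes it possible that multivitamin use will be recorded, but the plan does not ensure it.

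Finally, this is a single-visit, exploratory pilot with no hypothesis test. That limits the severity of the point, but descriptive results still depend on who was enrolled.

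**Conclusion.** The concern holds. The two lists agree on one item, conflict on one (age), have three criteria only in the synopsis and one exclusion only in Section 4.2, and place the STARS threshold in a different synopsis row. The difference that matters is the multivitamin restriction: following Section 4 as written admits current users of vitamin D-containing products to a study of serum vitamin D. The age, STARS and stage 3 and 4 differences are minor or explicable.

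The textual finding needs no assumption beyond the limit that only the available text could be searched for a rule of precedence. The washout comparison assumes first-order elimination at the protocol's stated half-life. The size of any distortion is unknown. This should be fixed before enrolment, but it does not invalidate the study.

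**What to change.** Reconcile the synopsis with Sections 4.1 and 4.2 into one identical list, with one age rule and the STARS threshold in both places. State explicitly:

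- whether family history and maculopathy are entry requirements (both, either or neither);
- whether the stage 3 and 4 exclusion applies;
- whether the multivitamin and vitamin D restriction applies.

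The choice of population is the sponsor's.

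Whatever is decided on the last item, record current multivitamin and vitamin D use at the existing visit. If users are permitted, or some are enrolled despite a restriction, they can then be identified and the vitamin D results shown with and without them. If the restriction is kept, the answer documents that it was applied.

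The cost is a wording amendment and one question, which could go on the paper CRF already planned. No extra subjects, visits or procedures are needed. On the illustrative counts above, leaving out 5 or 10 users widens the half-width by 0.6 or 1.4 points (14.0 − 13.4 and 14.8 − 13.4).

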## 2. Background and rationale

Age-related macular degeneration (AMD) is the leading cause of irreversible vision loss in industrialized countries; its incidence increases with life expectancy. Age-related macular

degeneration is a multifactorial disease, with environmental risk factors such as smoking, dietary habits, or obesity interacting with genetic determinants. According to that, a Simplified Thea AMD Risk-assessment Scale (STARS) was developed to detect individuals at high risk of AMD. The objective of the STARS questionnaire is to help the ophthalmologists to identify AMD risk factors to prevent AMD in clinical practice. It should be used also in general population to detect subjects at high risk for AMD (F066 EVER 2014). Another risk factor is dietary habits, and observational studies suggest that higher dietary intake of lutein-zeaxanthin,  $\omega$ -3 longchain, polyunsaturated fatty acids (DHA and EPA), or both are associated with a decreased risk of developing advanced AMD. In the retina, DHA increases mitochondrial activity and has anti-oxidative, anti-inflammatory, anti-apoptotic, and antiangiogenic effects. An imbalance in retinal lipids leads to photoreceptor degradation and the accumulation of lipid and lipoprotein debris in the retinal pigment epithelium layer. Because the continuous renewal of retinal membranes requires a constant supply of omega-3 fatty acids by retinal pigment epithelium cells, diets rich in DHA may improve retinal function and may delay the development of exudative AMD. Blood DHA concentrations were shown to be inversely related to other degenerative diseases of the retina, such as retinitis pigmentosa. Cho et al, showed a modest inverse associations between DHA intake and AMD in both men and women suggest a protective role of this fatty acid in the development of the disease. In addition, intake of fish, a major source of DHA, was inversely associated with AMD. Seddon et al confirm the previous observations in 2013 by showing that an increased self-reported dietary intake of  $\omega$ -3 fatty acids is associated with reduced risk of geography atrophy (GA) and may modify genetic susceptibility for progression to GA. Following micronutrients constitute the currently existing supplement formulae: vitamin C, vitamin E, lutein/zeaxanthin, zink oxide and cupric oxide. However the dosages as proposed in the aforementioned studies are not allowed in Europe, therefore there is increasing interest in adding other micronutrients with antioxidant properties and components with biological plausibility effect, such as omega-3, resveratrol, vitamin B and vitamin D.

Association between vitamin D status (as assessed by the serum 25(OH)D) and the risk of early or late AMD have been reported in several cross sectional studies. Two meta-analyses were performed recently. Annweiler et al. concluded that there is evidence that high blood 25(OH)D may be protective against AMD, especially late AMD. On the opposite, Wu et al. concluded that there is no evidence to indicate an inverse association between serum vitamin D levels and any stages and subtype of AMD risk. Thus, the association between vitamin D status and AMD needs additional assessments. However, there are experimental evidences suggesting that vitamin D inhibits the inflammatory reaction and angiogenetic process involved in the development of AMD. It will be interesting to conduct randomized controlled clinical trials to assess the effects of vitamin D supplementation in the development or progression of AMD.

More than 50% of the world's population is at risk for vitamin D deficiency and especially elderly individuals are at risk because of poor dietary vitamin D intake, reduce mobility, decreased exposure to sunlight and decline in renal function.

### 3. Trial objectives and Design

#### 3.1 Trial objectives

To detect individuals at high and moderate risk of AMD in the Belgium population and to perform a blood serum dosage of omega 3 , Vitamin D, zinc oxide and cupric oxide.

#### 3.2 Trial Design

Multi-centric, epidemiological and interventional survey

#### 3.3 Trial Flowchart

	Screen visit	
Informed consent	X	
STARS questionnaire	X	
Blood omega 3 dosage	X	
Blood Vit D dosage, zinc oxide and cupric oxide	X	
BCVA	X	
OCT	X	
Color fundus photography	X	

### 4. Selection and withdrawal of subjects

#### 4.1 Inclusion criteria

\* Subjects > 55 years

\* STARS questionnaire score  $\geq 10$  (moderate to high risk for AMD)

#### 4.2 Exclusion criteria

- Previous intake of eye nutritional supplements < 4 months prior to enrollment (half-life 25-OH D = 3-4 weeks, half-life of red blood cells: 100-120 days)
- STARS questionnaire score < 10 (low risk for AMD)
- Patient with AMD (stage 3 and 4)

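### The rules meant to keep supplement intake out of the omega-3 and vitamin D measurements differ between synopsis and Section 4.2, leave products uncovered, and rest on a justification that does not fit the stated specimen

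*Combined protocol and SAP*

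**What the plan says.** The combined protocol and SAP deals with supplement intake in two places.

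- Section 4.2 (Exclusion criteria) has one rule, "Previous intake of eye nutritional supplements < 4 months prior to enrollment", followed by its reason in brackets: "half-life 25-OH D = 3-4 weeks, half-life of red blood cells: 100-120 days". Section 4.1 (Inclusion criteria) does not mention supplements.
- Section 1 (Study Synopsis) repeats the eye-supplement rule with the same 4 months and adds "no current intake of multivitamins especially when containing Vit D". The added line has no look-back period.

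On the specimen, the purpose in the synopsis reads "Blood serum dosage of omega 3 and vitamin D in individuals with moderate and high risk of AMD", and Section 3.1 (Trial objectives) likewise plans "to perform a blood serum dosage of omega 3". The flowchart (Section 3.3) and the laboratory section (5.2) say only that blood is taken. No section says that omega-3 is measured in red cells.

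Neither the flowchart nor Sections 5.2 and 5.3 lists a supplement or diet history. There is one visit. Section 8.2 (Analysis) gives a table of vitamin D categories with cut-offs at 30, 50 and 125 nmol/L and specifies no summaries. Section 8.1 plans 50 subjects, no control group and no power calculation, with the results to inform a larger study.

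**The concern.** The bracketed reason shows what the exclusion is for: recent supplements should not contribute to the blood levels. Two things work against that aim.

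The first is product scope. Section 2 describes existing eye formulae as built on vitamins C and E, lutein/zeaxanthin, zinc and copper, and presents omega-3 and vitamin D as candidates for addition. So the one class that Section 4.2 excludes need not contain either primary analyte, while products that plainly do contain them are not named. A user of such a product who is enrolled has a raised level. Because Section 8.2 classifies vitamin D by fixed cut-offs, an upward shift moves subjects out of deficiency and insufficiency. With a single visit and no supplement history on the schedule, nothing planned would allow this to be examined afterwards, and the figures are meant to feed a bigger study.

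The second is the reasoning behind the 4 months. It relies on a red-cell figure for a measurement described as serum, and calls that figure a half-life when the interval is barely longer than one such half-life.

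**Working it through.** **1. Who is excluded, by product**

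| Product | Synopsis | Sections 4.1 and 4.2 |
|---|---|---|
| Eye supplement within 4 months | excluded | excluded |
| Multivitamin, current | excluded | not mentioned |
| Multivitamin, recently stopped | not excluded | not mentioned |
| Stand-alone vitamin D | not named | not named |
| Stand-alone omega-3 | not named | not named |

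The two places agree only on the first row. On the second, they lead to different enrolment decisions for the same person.

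**2. What the interval clears, on the plan's own figures**

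The plan states no target residual and no derivation, so there is no calculation of its own to reproduce. The check uses first-order decay: residual share of an increment = 0.5^(t / half-life).

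Inputs from Section 4.2: t = 4 months = 4 × 30.44 ≈ 121.75 days; 25-OH D half-life 3-4 weeks = 21-28 days; red-cell figure 100-120 days.

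| Quantity | Half-life (days) | Half-lives elapsed | Share left |
|---|---|---|---|
| 25-OH D | 21 | 121.75/21 = 5.80 | 1.8% |
| 25-OH D | 28 | 121.75/28 = 4.35 | 4.9% |
| Red cells, read literally | 100 | 121.75/100 = 1.22 | 43.0% |
| Red cells, read literally | 120 | 121.75/120 = 1.01 | 49.5% |

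The length assumed for 4 months matters little. At 120 days the red-cell residual is 43.5 to 50.0%; at 123 days it is 42.6 to 49.1%.

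If 100-120 days is a full duration instead, 121.75 days is just past its upper end and nothing remains. The result therefore turns on the word half-life.

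**3. A recently stopped multivitamin**

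The synopsis bars only current use. For someone who stopped 7 days before the visit (a timing chosen for illustration), the 25-OH D increment left is 0.5^(7/28) = 84% to 0.5^(7/21) = 79%.

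**4. Can the effect on the vitamin D categories be sized?**

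Not from the documents. They give no expected mean, SD, frequency of supplement use or size of increment. With assumed inputs only (unsupplemented mean 50 and SD 20 nmol/L; a share s of 10 to 30% of subjects carrying an extra 15 to 25 nmol/L), the share below 50 nmol/L is (1 − s) × 0.5 + s × Φ(−increment/20):

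- s = 0.1, increment 15: 0.45 + 0.1 × 0.227 = 0.47
- s = 0.3, increment 25: 0.35 + 0.3 × 0.106 = 0.38

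against 0.50 without users. This shows the direction of the bias. It does not estimate its size in this study, and the assumed mean lies exactly on the cut-off.

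**The case against.** Several parts of the case for the plan stand.

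- A reader might infer that the 4-month interval fails and leaves both primary levels inflated. The documents do not support this. The 43 to 49% needs the red-cell figure to be a true half-life and omega-3 to be measured in red cells. The stated specimen is serum, for which no omega-3 half-life is given. Four months is also just longer than 120 days, which fits an interval chosen to outlast a full duration. Even on the literal reading, the figure is a share of the supplement-derived red-cell increment, not a 43 to 49% rise in the measured level.
- For vitamin D from eye supplements, the interval works on the plan's own half-life. The vitamin D concern comes only from product scope.
- A reader might also infer that nothing bars vitamin D products outside eye formulae. The synopsis does bar current multivitamins, and a site reading the whole document may apply that line.
- The fall to 38-47% rests on assumed inputs. With 50 subjects the 95% half-width around 50% is 1.96 × √(0.25/50) = 14 percentage points, so a shift of 3 to 12 points lies within sampling error. But sampling error does not remove a bias in a known direction, and the exploratory label does not either.
- No comparison by risk level is planned, so confounding of supplement use with risk status is not the issue here.

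It can also be said that sites must ask about eye supplements to apply Section 4.2, and that the electronic patient file may hold other products. Nothing requires either to be recorded as study data.

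**Conclusion.** The point holds as an inconsistency and a gap in the eligibility rules, with a separate defect in the stated justification.

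The synopsis and Section 4.2 disagree on multivitamins, neither names stand-alone vitamin D or omega-3 products, and supplement use is not on the visit schedule. Current users can therefore be enrolled by a site that follows Section 4.2. The direction of the bias is clear, assuming that such products raise the measured levels: omega-3 and vitamin D are overstated, and deficiency and insufficiency are understated. Its size depends on how many users are enrolled, which the documents do not indicate.

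The bracketed reason needs correcting on either reading. If 100-120 days is a half-life, 4 months is 1.0 to 1.2 half-lives and the figure does not support the interval for a red-cell measurement. If it is a full duration, the interval just covers it and the label is wrong. The documents cannot settle which. In both cases a red-cell figure does not justify an interval for a serum measurement. It does not follow that the stated omega-3 measurement is contaminated by eye supplements. For 25-OH D, with 2 to 5% of an increment left, the interval is adequate.

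**What to change.** 1. Reconcile Section 1 with Section 4.2, so that Section 4.2 carries the multivitamin criterion and says how stand-alone vitamin D and omega-3 products are handled. The sponsor should state and justify any look-back interval; none is proposed here.
2. State in Sections 3.1 and 5.2 whether omega-3 is measured in serum or red cells. In Section 4.2, say whether 100-120 days is a half-life or a full duration, and make the reason refer to the specimen actually measured.
3. Add supplement history to the flowchart, and record product and date of last intake on the CRF.
4. In Section 8.2, specify the omega-3 and vitamin D summaries, including the share in each vitamin D category, for all subjects and again for those with no recorded supplement use.

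The cost is some wording, two CRF fields and one extra table. A few otherwise eligible subjects may be lost, and with 50 planned the non-user summary will be less precise than the overall one.

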#### 4.3 Expected duration of trial

1 visit

### 5. Trial Procedures

#### 5.1 By visit

One single study visit

#### 5.2 Laboratory tests

One blood sample for omega 3 , Vitamin D dosage, zinc oxide and cupric oxide

#### 5.3 Other investigations

Visual acuity assessment, OCT scan, Color fundus photography, stars questionnaire.

### 6. Assessment of efficacy

Not applicable, no treatment will be administered

### 7. Assessment of Safety

Not applicable, no treatment will be administered

### 8. Statistics

#### 8.1 Sample size

We anticipate to include 50 subjects to this pilot study. There is no control group and it is an exploratory study, so no power calculation has been done. The study results will provide us trends to build a bigger study.

